7.9.2. Individual Stopping Rules

In addition to the above stated group holding rules, stopping rules will apply for individual volunteers in the occurrence of a serious adverse event considered by the investigator to be at least possibly related to the study drug. This applies to both solicited and unsolicited events as well as to laboratory parameters.

In addition to these pre-defined criteria, the study can be put on hold upon advice of the Chief Investigator, Study Sponsor, regulatory authority, Research Ethics Committee (REC) or Local Safety Committee (LSC), for any single event or combination of multiple events which, in their professional opinion, jeopardise the safety of the volunteers or the reliability of the data.

7.10. Local Safety Committee

A Local Safety Committee (LSC) will be appointed to provide real-time safety oversight. The LSC will review SAEs deemed possibly, probably or definitely related to study interventions. The LSC will be notified within 24 hours of the Investigators' being aware of their occurrence. The LSC has the power to place the study on hold if deemed necessary following a study intervention-related SAE. In addition to the LSC chair (LSM), there will be a minimum of two other appropriately qualified committee members. LSC membership details can be found in the *LSC Terms of Reference*. All correspondence between Investigator and LSC will be conveyed by the Investigator to the trial Sponsor.

The chair of the LSC may be contacted for advice and independent review by the Investigator or trial Sponsor in the following situations:

- Following any SAE deemed to be possibly, probably, or definitely related to a study intervention.
- Any other situation where the Investigator or trial Sponsor feels independent advice or review is important.

The study can be put on hold upon advice of the Chief Investigator, Study Sponsor, REC or Local Safety Committee, for any single event or combination of multiple events which, in their professional opinion, jeopardise the safety of the subjects or the reliability of the data. If the study is placed on hold it may only be restarted following discussion with and approval from the LSC, the REC, the trial Sponsor and Chief Investigator. If the clinical trial is halted and is unable to resume, a formal letter will be sent to the regulatory authorities by the Sponsor explaining the reasons for cessation of the study.

7.11. Safety Profile Review

The safety profile will be assessed on an on-going basis by the Investigators. The Chief investigator, Principal Investigator, and relevant Investigators (as per the trial delegation log) will also review safety issues and SAEs as they arise.

7.12. Safety Reports and Dissemination Rules

Analyses presented to the local safety committee will be based on electronic case report form (eCRF) pages entered into the database. Additional data may be provided in narrative format by the study investigators of the study site. Data to be used for local safety committee review will be monitored prior to presentation to the committee using 100% source data verification. Information that will be included in safety reports and presented to the local safety committee at each meeting is documented in the *Local Safety Committee (LSC) Terms of Reference*

The local safety committee's decision, following review of the data presented, will be disseminated to the chief investigator, sponsor and key representatives of the trial management group. The signed safety report will be stored in the trial master file (TMF).

7.13. Emergency contact - 24 hours

Volunteers will be encouraged to contact one of the investigators on the 24 hour emergency mobile study telephone number if they develop any symptoms between the regular follow up visits. The investigator will consider an extra clinical review if the volunteer has any symptoms that are moderate or severe.

8. Statistics

A statistical analysis plan will be produced prior to patient enrolment. The final SAP will be signed off prior to final analyses at the end of trial.

8.2 Statistical analyses

A statistical analysis plan will be produced prior to patient enrolment. This may affect the analyses that can subsequently be done – this will be documented in a revised statistical analysis plan.

Analysis of the safety and immunogenicity endpoints as detailed in **Section 2** will be performed primarily using descriptive statistics. Analysis will be as treated for safety endpoints and per protocol for immunogenicity.

The proportion of patients experiencing each adverse event observed, including biochemical and haematological samples outside the laboratory reference ranges, after each vaccine dose will be calculated and tabulated. For antibody measures means / medians, geometric means and geometric mean fold changes, with 95% confidence intervals will be calculated at each time point, Antibody data will also be described graphically through plotting titres at each time points for each group. The study is not powered for precise comparison of groups but for quantitative measures a non-parametric comparison will be done using either a Mann-Whitney

U test for between-group analyses or, for paired data between time points (e.g. baseline and post vaccination) using Wilcoxon matched pairs test (i.e. comparing numbers that increase vs decrease). If, on a log-scale antibody data are approximately normally distributed then comparison by t-tests and paired t-tests may also be done with adjustment for baseline levels if necessary.

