1.4 Pre-clinical studies of pEVAC-PS

1.5. Dose Rationale

The CE-marked PharmaJet Tropis intradermal (ID) delivery of DNA has demonstrated to be highly effective at reducing the dose required for anti-viral responses in several different systems. An adaptive dose escalation regime follows to discover the lowest dose of DNA which will produce an effective immune response when delivered intradermally, with potential doses of 1.2mg, 0.8mg, 0.4mg and 0.2mg.

Objective	Outcome measure			
Primary To assess the safety and reactogenicity of a new pan-Sarbeco Coronavirus DNA candidate vaccine pEVAC-PS in a boosting regime in healthy volunteers.	 a) Occurrence of solicited local reactogenicity signs and symptoms for 7 days following vaccination; b) Occurrence of solicited systemic reactogenicity signs and symptoms for 7 days following vaccination; c) Occurrence of unsolicited adverse events (AEs) for 28 days following vaccination; d) Change from baseline for safety laboratory measures and; e) Occurrence of disease enhancement episodes 			
Secondary To assess the humoral immunogenicity of pEVAC-PS when administered to healthy volunteers as a booster vaccine, through the analysis of SARS-CoV and SARS-CoV-2 RBD antibody titres. To assess the humoral immunogenicity of the candidate vaccine pEVAC-PS at 28 days (4 weeks) after 2 doses of pEVAC-PS have been administered 28 days apart, given by needle-free technology (PharmaJet); both administered in split doses, left and right deltoids (when >0.2mg)	 a) Serology: receptor binding domain (RBD) responses in the majority of vaccinees per group for SARS-CoV and SARS-CoV-2 			
Secondary Assess optimum dosing of candidate vaccine pEVAC-PS	a) Compare dose tolerability and results of immunogenicity of up to four different doses of PharmaJet ID			

2. Objectives and Endpoints

	administration at 28 days (4 weeks)
	after the second dose of vaccine
Secondary	a) Serology: receptor binding domain
To assess long term (up to 12 months)	(RBD) for SARS-CoV and SARS-
humoral immunogenicity of the candidate	CoV-2 RBD pre and post-
vaccine pEVAC-PS administered by the	immunisation.
needle-free technology (PharmaJet)	
administered as 2 doses (split L&R	
when >0.2mg)	

3. Study Design

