3.3. Description of Study Cohorts

There will be up to study groups in the trial, with a total of up to 36 volunteers.

Stage 1	Group 1a	6 volunteers; 2 doses of pEVAC-PS at 0.2mg intradermally on Day 0 and Day 28.
	Subgroup 1a- expanded	12 volunteers; 2 doses of pEVAC-PS at 0.2mg intradermally on Day 0 and Day 28.
Stage 2	Group 2a	9 volunteers; 2 doses of pEVAC-PS at 0.4mg OR 0.8mg intradermally on Day 0 and Day 28.
	Group 2b	9 volunteers; 2 doses of pEVAC-PS at 0.8mg OR 1.2mg intradermally on Day 0 and Day 28.
	Group 2c If the target is not met from group 2a or 2b (0.8mg)	12 volunteers; 2 doses of pEVAC-PS 1.2mg intradermally on Day 0 and Day 28
Stage 3	Group 3 If primary immunogenicity target is met during Stage 2	12 volunteers; 2 doses of pEVAC-PS at the most well tolerated and immunogenic dose from Group 2a or 2b on Day 0 and Day 28.
	If the immunogenicity targets are not met by 1.2mg in group 2b, no further participants will be enrolled.	

Table 1: Study groups.

Figure 1. Study Flow Diagram

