5.2 Schedule of events

Table 2. Schedule of events

Attendance Number	1 ^s	2	3	4	5	6	7	8	9	10	11	12 [†]	COVID-19 Testing
Timeline** (days)	≤90	0	1	3	7	14	28	42	56	84	182	365	As required
Time window (days)				±1	±2	±3	±7	±3	±7	±3	±14	± 28	N/A
Informed Consent	Х												
Review eligibility criteria	Х	х					Х						
Vaccination (IM)		Х					Х						
Vital signs^	Х	Х		Х	Х	Х	Х	Х	Х	Х	Х	Х	х
Height and weight	Х												
Telephone/Video call			Х										
Ascertainment of adverse events and con meds		Х	Х	Х	Х	Х	Х	Х	Х	Х	Х	Х	Х
Diary cards provided		Х					Х						
Diary cards reviewed			Х	Х	Х	Х	Х	Х	Х				
Medical History, Physical Examination	Х	(X)		(X)	(X)	(X)	(X)	(X)	(X)	(X)	(X)	(X)	(X)
Biochemistry, Haematology (mL)	5	5		5	5		5	5					5
Exploratory immunology (mL)		50			50	50	50	50	50	50	50	50	up to 50
Nose/Throat Swab													Х
Urinalysis	х												
Urinary bHCG (women only)	Х	Х					х						
HBsAg, HCV Ab, HIV serology (mL)	5												
Blood volume per visit	10	61.5		5	55	50	55	55	50	55	50	50	up to 57.5
Cumulative blood volume [%]	10	71.5		76.5	131.5	181.5	236.5	291.5	341.5	396.5	446.5	496.5	554

S=screening visit; (X) = if considered necessary ^ = Vital signs includes pulse, blood pressure and temperature; ** Timeline is approximate only. Exact timings of visits relate to the day on enrolment, i.e., each visit must occur at indicated number of days after enrolment ± time window. % Cumulative blood volume for volunteers if blood taken as per schedule, and excluding any repeat safety blood test that may be necessary. [†]Only for the final group which are enrolled

.

Table 3: Schedule of Events for Unscheduled and Early Termination Visits. Applicable for

 both all groups

	Unscheduled Visit Following AE	Early Termination Visit
Medical History	(x)	(x)
Physical Examination	(X) ¹	(x)
ECG	(x)	
Urinalysis	(x)	
Physical Observations	х	х
Concomitant medications	х	х
AEs reviewed	х	х
Diary card review ²	х	(x)
Haematology (mL)	3	3
Biochemistry (mL)	5	5
Coagulation (mL)	(2.7)	(2.7)

(x) = If considered necessary, emphasising any acute complaints.

¹ A full physical examination or symptom directed physical examination can be carried out at the discretion of the investigator.

² Required if the participant is currently within the diary card completion phase of the study only.

The above schedule is not an exhaustive list; procedures carried out will be guided by clinical need and will be at the discretion of the investigator.

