7.6. Reporting procedures for AEs, SAEs and other safety events

7.6.1 Reporting Procedures for AEs

All AEs occurring in the 28 days following each vaccination observed by the Investigator or reported by the volunteer, whether or not attributed to study medication, will be recorded. AEs deemed to be not serious by the investigator will be recorded in the site's AE log and on the eCRF by the study team within 5 days of the study visit. AE data will be made available to the LSC before each interim safety analysis.

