8.3 Procedure for accounting for missing, unused and spurious data

Missing data will not be imputed. Patients with data missing on any variable required for a given analysis will be excluded from that analysis only. Outliers will be checked but not excluded if data errors are not found. Where results are reported as below or above assay limits a value of half or double the limit will be assigned for quantitative calculations. Antibody data will be logged for presentation or presented on log-scaled axis.

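### Section 8.2 tabulates out-of-range laboratory results per patient after each dose, but Table 2 schedules two or three safety samples after dose 1 and one after dose 2, so the two proportions are not comparable

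*Protocol*

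**What the plan says.** Section 8.2 sets the laboratory summary: "The proportion of patients experiencing each adverse event observed, including biochemical and haematological samples outside the laboratory reference ranges, after each vaccine dose" is to be calculated and tabulated. The unit is the patient and the split is by dose.

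Table 1 (Section 3.3) gives the dosing days, for example "6 volunteers; 2 doses of pEVAC-PS at 0.2mg intradermally on Day 0 and Day 28" for the first group; every other group has the same two days. The biochemistry and haematology row of Table 2 (Section 5.2) has a 5 mL entry at screening and on Days 0, 3, 7, 28 and 42, plus the as-required COVID-19 visit. It has none on Days 14, 56, 84, 182 or 365. Visits are timed from enrolment: "each visit must occur at indicated number of days after enrolment ± time window".

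Adverse events have equal windows. Section 7.6.1 records "All AEs occurring in the 28 days following each vaccination observed by the Investigator". On missing data, Section 8.3 says "Missing data will not be imputed", which does not bear on samples that were never scheduled. Neither 8.2 nor 8.3 allows for a different number of samples after each dose.

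**The concern.** A laboratory abnormality can be seen only when blood is drawn. A proportion of patients with any out-of-range value therefore depends on how many samples each patient gives, as well as on the risk per sample. The planned table puts a period with two or three scheduled samples beside a period with one, as if observation were equal. The symptom and adverse event rows of the same table do rest on equal 28-day periods, so a reader has no cue that the laboratory rows differ.

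This is a first-in-human, two-dose study that reports safety descriptively. A table that tends to show fewer laboratory abnormalities after dose 2 for reasons of sampling alone could be taken as reassurance about the second dose. The timing differs too: +3, +7 and +28 days after dose 1 against a nominal +14 days after dose 2, so a short-lived early change after dose 2 could be missed. How abnormality is defined does not matter here; the imbalance is the same under reference ranges or the grades of Table 10.

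**Working it through.** **Step 1: which days carry a safety sample.** The itemised volumes in Table 2 (safety, immunology and, at screening, virus serology) were summed and set against the row "Blood volume per visit".

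| Visit | Itemised sum (mL) | Stated (mL) |
|---|---|---|
| Screening | 5 + 5 = 10 | 10 |
| Day 0 | 5 + 50 = 55 | 61.5 |
| Day 3 | 5 | 5 |
| Day 7 | 5 + 50 = 55 | 55 |
| Day 14 | 50 | 50 |
| Day 28 | 5 + 50 = 55 | 55 |
| Day 42 | 5 + 50 = 55 | 55 |
| Day 56 | 50 | 50 |
| Day 84 | 50 | 55 |
| Day 182 | 50 | 50 |
| Day 365 | 50 | 50 |

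The stated volumes add to the table's own cumulative 496.5 mL, and 496.5 + 57.5 = 554 mL with a COVID-19 visit. Days 3 to 56 agree with the row entries. Day 0 is 6.5 mL over its items and Day 84 is 5 mL over.

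**Step 2: samples per dose.** After dose 1: Days 3, 7 and 28, so three, if the Day 28 bleed precedes the second injection. That is the natural reading, but Section 5.5.1 does not state the order. If Day 28 is not credited to dose 1, the count is two. After dose 2: Day 42 only. By the windows, dose 2 falls on Days 21 to 35 and the Day 42 visit on Days 39 to 45, so the sample lies 39 − 35 = 4 to 45 − 21 = 24 days after dose 2.

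**Step 3: effect on the proportion.** Let p be the chance that one sample is out of range, equal after both doses. The protocol gives no such rate, so p is assumed. With k independent samples, P(at least one) = 1 − (1 − p)^k.

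| p | Dose 2 (k = 1) | Dose 1 (k = 2) | Dose 1 (k = 3) | Ratio 2:1 | Ratio 3:1 |
|---|---|---|---|---|---|
| 1% | 1% | 1.99% | 2.97% | 1.99 | 2.97 |
| 5% | 5% | 9.75% | 14.3% | 1.95 | 2.85 |
| 10% | 10% | 19.0% | 27.1% | 1.90 | 2.71 |
| 20% | 20% | 36.0% | 48.8% | 1.80 | 2.44 |

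Results within a person are correlated, which shrinks the gap. Under a beta-binomial with intra-person correlation r, P(at least one) = 1 − B(a, b + k)/B(a, b), with a = p(1 − r)/r and b = (1 − p)(1 − r)/r. At p = 5%, against 5% for dose 2:

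| r | Dose 1 (k = 2) | Dose 1 (k = 3) | Ratio 2:1 | Ratio 3:1 |
|---|---|---|---|---|
| 0.2 | 8.8% | 11.8% | 1.8 | 2.4 |
| 0.5 | 7.4% | 8.9% | 1.5 | 1.8 |
| 0.8 | 5.95% | 6.5% | 1.2 | 1.3 |

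The ratio reaches 1 only if each person's results are identical across samples.

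**Step 4: in patients.** For the 21 participants that Section 8.1 foresees at the selected dose, p = 5% with three independent samples gives 21 × 0.1426 = 3.0 expected patients after dose 1 and 21 × 0.05 = 1.05 after dose 2. In a group of nine it is 9 × 0.1426 = 1.3 against 0.45.

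**Step 5: check of the remedy.** With equal numbers of samples the artefact goes: at p = 5%, one against one is 5% and 5%, and three against three is 14.3% and 14.3%. A by-visit proportion has k = 1 everywhere.

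**The case against.** The strongest reply is that the protocol makes no comparison between dose 1 and dose 2. Section 8.1 plans no formal test of the primary outcomes, and 8.2 is mainly descriptive. The comparative objective in Section 2 is between dose levels, and every group follows the same Table 2, so that comparison is untouched. This stands, and it limits the harm to how one descriptive table reads.

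It is tempting to say that primary outcome (d) is biased. The documents do not support that. Outcome (d) is "Change from baseline for safety laboratory measures", a different quantity from the proportion out of range, and the number of samples does not distort it in this way.

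It is also tempting to say that the table will show fewer abnormalities after dose 2. That holds only in expectation. Take three independent samples against one and treat the two counts as independent binomials. The chance that dose 1 actually shows more patients with a given abnormality is then 32% (n = 6, p = 2.5%), 49% (n = 6, p = 5%) and 59% (n = 9, p = 5%). A true dose 2 effect could also offset the artefact.

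Nor is the first week after dose 2 strictly unsampled. The windows allow a sample from four days after dose 2, and Table 3 provides bloods at unscheduled visits after an adverse event. What is true is that no routine sample is nominally due in that week. If the extra 5 mL at Day 84 is an unlisted safety tube, it would come 56 days after dose 2, outside the adverse event window, and give at most three against two.

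Finally, table layout often belongs in the SAP, which is not shown and may well tabulate by visit. That lowers the weight of the point but does not remove it, because the protocol itself names the per-dose patient proportion.

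**Conclusion.** The point holds in a limited form. The per-dose laboratory proportions in 8.2 rest on unequal scheduled observation: three samples (or two) after dose 1 and one after dose 2. At equal risk per sample the dose 1 proportion is inflated in expectation by a factor of roughly 1.2 to 3. The sample counts come from the protocol. The factor rests on assumed per-sample rates of 1% to 20%, on intra-person correlation from 0 to 0.8, and on whether the Day 28 bleed is credited to dose 1.

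A reader might infer that the trial's safety conclusion or its choice of dose is biased. Neither follows: no inference between doses is planned, and dose levels share one schedule. What is at stake is a descriptive safety table that invites a wrong reading and is easily repaired.

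**What to change.** In Section 8.2, replace the per-dose laboratory proportion with a table by scheduled visit (Days 3, 7, 28 and 42), using as denominator the number of participants sampled at that visit. Add that per-dose proportions with any laboratory abnormality are not comparable between dose 1 and dose 2, and that no routine safety sample is nominally scheduled in the first week after dose 2.

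In Table 2, reconcile the volumes at Day 0 (61.5 mL stated, 55 mL itemised) and Day 84 (55 mL stated, 50 mL itemised), so that the safety-sample days are unambiguous.

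The cost is wording and a table correction. No added sampling is needed to remove the artefact. Extra safety tubes at Days 14 and 56 would be a schedule preference and would still leave the first week after dose 2 without a nominal sample.

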7.1. Safety definitions

Adverse Event (AE)

An AE is any untoward medical occurrence in a volunteer, including a dosing error, which may occur during or after administration of the vaccine and does not necessarily have a causal relationship with the intervention. An AE can therefore be any unfavourable and unintended sign (including an abnormal laboratory finding), symptom or disease temporally associated with the study intervention, whether or not considered related to the study intervention.

Adverse Reaction (AR)

An AR is any untoward or unintended response to the vaccine. This means that a causal relationship between the inoculum and an AE is at least a reasonable possibility, i.e., the relationship cannot be ruled out. All cases judged by either the reporting medical investigator or the sponsors as having a reasonable suspected causal relationship to the inoculum (i.e. possibly, probably or definitely related to the inoculum) will qualify as adverse reactions.

Unexpected Adverse Reaction (UAR)

An adverse reaction, the nature or severity of which is not consistent with the applicable information about the vaccine in the protocol, is considered as an unexpected adverse reaction.

Serious Adverse Event (SAE)

An SAE is an AE that results in any of the following outcomes, whether or not considered related to the study intervention.

- Death (i.e., results in death from any cause at any time)
- Life-threatening event (i.e., the volunteer was, in the view of the investigator, at immediate risk of death from the event that occurred). This does not include an AE that, if it occurred in a more serious form, might have caused death.
- Persistent or significant disability or incapacity (i.e. substantial disruption of one's ability to carry out normal life functions).
- Hospitalisation other than admission in the NIHR-CRF, regardless of length of stay, even if it is a precautionary measure for continued observation. Hospitalisation (including inpatient or outpatient hospitalisation for an elective procedure) for a pre-existing condition that has not worsened unexpectedly does not constitute a serious AE.

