7.5.2 Assessment of Severity

The severity of clinical and laboratory adverse events will be assessed according to the scales in **Tables 7-10**.

Adverse Event	Grade	Intensity
Pain at injection site	1	Pain that is easily tolerated
	2	Pain that interferes with daily activity
	3	Pain that prevents daily activity
Erythema at injection site*	1	>3 - ≤ 50mm
	2	>50 - ≤100mm
	3	>100mm
Swelling at injection site*	1	>3 - ≤ 20mm
	2	>20 - ≤ 50mm
	3	>50mm
Itching at injection site	1	Itching that is easily tolerated
	2	Itching that interferes with daily activity
	3	Itching that prevents daily activity

* erythema or swelling ≤3mm is an expected consequence of skin puncture and will therefore not be considered an adverse event

Table 8:	Severity	grading	for p	hysical	observations

Adverse Event	Grade 1 (mild)	Grade 3 (severe)			
Fever (oral)	37.6°C - 38°C 38.1°C - 39°C		>39°C		
Tachycardia (bpm)*	101-115	101-115 116-130			
Bradycardia (bpm)**	50-54	40-49	<40		
Systolic Hypertension (mmHg)	141-159 160-179		≥180		
Diastolic Hypertension (mmHg)	91-99	100-109	≥110		
Systolic Hypotension (mmHg)***	85-89	80-84	<80		

*Taken after ≥10 minutes at rest

** When resting heart rate is between 60-100 beats per minute. Use clinical judgement when characterising bradycardia among some healthy subjection populations, for example, conditioned athletes.

*** Only if symptomatic (e.g. dizzy / light headed)

Table 9: Severity grading criteria for local and systemic AEs

Grade	Criteria
GRADE 0	None; Symptom not experienced
GRADE 1	Mild: Short-lived or mild symptoms; medication may be required. No limitation to usual activity
GRADE 2	Moderate: Mild to moderate limitation in activity. Medication may be required
GRADE 3	Severe: Considerable limitation in activity. Medication or medical attention required

Routine Haematology		Lab Range	Grade 0	Grade 1	Grade 2	Grade 3	
	Male		130 - 170	126 - 170	115 - 125	100 - 114	<100
Haemoglobin	Female	g/i	120 - 150	114 - 150	103 - 113	90 - 104	<90
White blood	Elevated				11.50 - 15.00	15.01 - 20.00	>20
cells	Low	x10 ⁹ /I	4.00 - 11.00	3.51 - 11.49	2.50 - 3.50	1.50 - 2.49	<1.50
Platelets		x10 ⁹ /l	150 - 400	136 - 400	125 - 135	100 - 124	<100
Neutrophils		x10 ⁹ /l	2.0 - 7.5	1.5 - 7.5	1.00 - 1.49	0.50 - 0.99	<0.50
Lymphocytes		x10 ⁹ /I	1.5 - 4.0	1.0 - 4.0	0.75 - 0.99	0.50 - 0.74	<0.50
Eosinophils		x10 ⁹ /l	0.0 - 0.5	0.0 - 0.64	0.65 - 1.50	1.51 - 5.00	>5.00
Routine Biochemistry			Lab Range	Grade 0	Grade 1	Grade 2	Grade 3

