7.8. Procedures to be followed in the event of abnormal findings

Eligibility for enrolment in the trial in terms of laboratory findings will be assessed as detailed in Appendix A. Abnormal clinical findings from medical history, examination or blood tests will be assessed as to their clinical significance throughout the trial. Laboratory adverse events will be assessed using the details in Table 10. If a test is deemed clinically significant, it may be repeated to ensure it is not a single occurrence. If a test remains clinically significant, the volunteer will be informed, and appropriate medical care arranged as appropriate and with the permission of the volunteer. Decisions to exclude the volunteer from enrolling in the trial or to withdraw a volunteer from the trial will be at the discretion of the Investigator.

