Appendix A: Laboratory Values for Exclusion

Laboratory parameters for inclusion/exclusion in the trial will be considered on an individual basis, with investigator discretion for interpretation of results and the need for repeated or further tests. In general, volunteers will be excluded if a result at screening constitutes what would qualify as a grade 1 (or higher) laboratory adverse event, according to the site-specific laboratory adverse event tables (filed in the TMF). Urinalysis at screening will be assessed as per the table below:

URINE ANALYSIS (using MULTISTIX)				
Protein*	2+ or Protein creatinine ratio of ≥50mg/mmol			
Blood£	2+ on two dipstick tests			
Glucose	1+			

*In the event of the dipstick testing positive for protein with $\geq 1 + \text{ protein urine should be sent for a protein creatinine ratio.}$

 ϵ In the event of urine dipstick testing positive for \geq 1+ blood with, or without, protein in volunteers a repeat dipstick test will be carried out to confirm haematuria. In female volunteers, a menstrual history will be taken to elicit whether the subject is currently menstruating and if they are, urine dipstick will be repeated after 1 - 2 weeks. If blood and/or proteinuria persist in any volunteer, an interpretation of the results will be undertaken by the investigator on an individual basis to determine if they will be excluded from the trial, and the appropriate follow-up arranged.

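### Section 8.2 counts every out-of-range laboratory sample as an adverse event, while Table 10 gives many of the same results Grade 0

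*Protocol*

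**What the plan says.** Section 8.2 of the protocol sets the counting rule for the safety tables. It tabulates, for each dose, the proportion of patients with each observed adverse event, "including biochemical and haematological samples outside the laboratory reference ranges". It attaches no condition on the Day 0 value.

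The safety chapter uses a different yardstick. Section 7.5.2 states: "The severity of clinical and laboratory adverse events will be assessed according to the scales in" Tables 7 to 10. Section 7.8 repeats it for laboratory results: "Laboratory adverse events will be assessed using the details in Table 10". Table 10 prints the laboratory range and a Grade 0 band in adjacent columns.

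Three other places bear on the point:

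- Section 2 lists, as primary outcome (d), "Change from baseline for safety laboratory measures". Section 8.2 brings this in through its opening words, "Analysis of the safety and immunogenicity endpoints as detailed in" Section 2.
- Section 7.1 defines an adverse event as "including an abnormal laboratory finding", without saying which scale decides what is abnormal.
- Appendix A says that volunteers will in general be "excluded if a result at screening constitutes what would qualify as a grade 1 (or higher) laboratory adverse event". It leaves room for investigator discretion and cites site-specific grading tables held in the trial master file, as Section 5.4.2 also does.

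**The concern.** One laboratory result can be an adverse event under one section and a non-event under another. The person preparing the primary safety table must choose which to follow, and either choice departs from the protocol. If 8.2 is followed, the table takes in results that the protocol's own scale grades 0 or does not grade, and values that the participant already had before vaccination.

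The trial has no control group, so no comparison column shows how many such results arise without vaccine. The event proportions belong to the primary safety objective, and Section 8.1 says that dose-adaptation decisions will draw on tolerability information.

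**Working it through.** The protocol states no figure here, so there is nothing to reproduce. The check compares the two rules and then illustrates the size of the difference.

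**1. Laboratory range against Grade 0 (Table 10)**

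| Parameter | Lab range | Grade 0 | Out of range, yet Grade 0 |
|---|---|---|---|
| Hb, male | 130–170 | 126–170 | 126–129 |
| Hb, female | 120–150 | 114–150 | 114–119 |
| White cells | 4.00–11.00 | 3.51–11.49 | 3.51–3.99; 11.01–11.49 |
| Platelets | 150–400 | 136–400 | 136–149 |
| Neutrophils | 2.0–7.5 | 1.5–7.5 | 1.5–1.9 |
| Lymphocytes | 1.5–4.0 | 1.0–4.0 | 1.0–1.4 |
| Eosinophils | 0.0–0.5 | 0.0–0.64 | 0.51–0.64 |
| Potassium | 3.5–5.3 | 3.4–5.3 | 3.4 |
| Urea | 2.5–7.8 | 2.5–8.1 | 7.9–8.1 |
| Creatinine | 53–97 | 53–106 | 98–106 |
| Bilirubin (normal LFT) | 0–20 | 0–25 | 21–25 |
| ALT/AST, male | 10–40 | 10–49 | 41–49 |
| ALT/AST, female | 7–35 | 7–43 | 36–43 |
| ALP (row label lost in the extracted text) | 30–130 | 30–142 | 131–142 |
| Albumin | 35–50 | 32–50 | 32–34 |

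All 15 rows have such a zone. The sodium row is broken in the text and is not counted. INR, a coagulation test outside the routine panel, has identical columns.

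**2. Results with no grade.** Magnesium and cholesterol are measured (Section 5.3.5) but do not appear in Table 10. High Hb, platelets, neutrophils and lymphocytes have no grade either. Section 8.2 would count all of these when out of range.

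**3. Pre-existing values.** Take a neutrophil count of 1.8 at screening, on Day 0 and throughout. It is Grade 0, so Appendix A would not ordinarily exclude it, provided that the site-specific tables agree with Table 10. Under 8.2 it is an event after dose 1 and again after dose 2. Under outcome (d) its change is zero.

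**4. Size for a single analyte.** Table 2 schedules safety bloods on Days 0, 3, 7, 28 and 42. Assuming that the Day 28 sample is drawn before the second injection, three samples follow dose 1 (Days 3, 7, 28) and one follows dose 2 (Day 42). Let q be the chance that a healthy result is out of range; q is an assumption, not a protocol figure. With independent samples, the chance of at least one flag in k samples is 1 − (1 − q)^k.

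| q | After dose 2 (k = 1) | After dose 1 (k = 3) |
|---|---|---|
| 1% | 1% | 1 − 0.99³ = 3% |
| 2.5% | 2.5% | 1 − 0.975³ = 7% |
| 5% | 5% | 1 − 0.95³ = 14% |

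At q = 5% in a group of 6, that is 6 × 0.143 = 0.9 people expected after dose 1 and 6 × 0.05 = 0.3 after dose 2, for one analyte and with no vaccine effect. If values were fully repeatable within a person, both columns would be 5%, so the dose 1 figure lies between 5% and 14%. If Day 28 counted towards dose 2, each dose would have two samples and both figures would be 1 − 0.95² = 9.8%.

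**5. Effect of using Table 10.** Assume a normal distribution with the laboratory range as its central 95%, so mean = midpoint and SD = width/3.92. For platelets the mean is 275 and the SD is 250/3.92 = 63.8. The share below 136 is Φ((136 − 275)/63.8) = Φ(−2.18) = 1.5%, against 2.5% below 150. On the same basis the widened tail falls from 2.5% to 1.0% for neutrophils and to 0.3% for creatinine.

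**6. A slip inside Table 10.** Female Hb grade 1 is 103–113 and grade 2 is 90–104, so 103–104 g/l carries both grades.

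**The case against.** The strongest reply is that a first-in-human trial may reasonably tabulate every out-of-range result, that the adverse event definition in Section 7.1 is broad enough to allow it, and that the current rule captures high-side abnormalities that Table 10 cannot grade. Treatment-emergent definitions and shift tables are usually left to the SAP, which is not shown. Raw values are kept, so regrading at analysis loses nothing.

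Much of this stands. Broad display is sensible, and a change that hid ungraded results would be a step backwards. The absence of a treatment-emergent definition is not itself a fault of the protocol. What does not fall away is that 8.2 fixes a counting rule and labels its results as adverse events, while 7.5.2 and 7.8 assess laboratory adverse events by Table 10. A SAP cannot follow both.

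A reader might infer three stronger points, which the protocol does not support:

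- **That the safety analysis ignores baseline.** It does not. Outcome (d) is change from baseline, 8.2 covers the Section 2 endpoints, and 8.2 offers paired comparisons for quantitative measures. Only the event tabulation lacks a Day 0 condition.
- **That half or more of participants would be flagged.** With 14 independent analytes, 1 − 0.95^14 = 51% for one sample, and over four samples 1 − 0.95^56 = 94%. These describe a composite of any abnormality in any analyte. Section 8.2 tabulates each event separately, after each dose.
- **That escalation or holding would be triggered.** The holding rules in 7.9.1 turn on serious related events and the stage rules in 3.1.1 on antibody responders. Neither uses this count.

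**Conclusion.** The contradiction is real and can be read directly from the text: Grade 0 extends beyond the laboratory range in all 15 rows compared, and some measured parameters and directions have no grade. As worded, 8.2 reports Grade 0, ungraded and stable pre-existing results as events after vaccination.

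The distortion is moderate and works analyte by analyte. With q = 5% and independent samples, up to 14% of people are flagged after dose 1 and 5% after dose 2; with q = 1% the figures are 3% and 1%. The gap between doses reflects the number of samples taken, and correlation between samples would narrow it. These percentages rest on assumed q and independence; the contradiction does not. It should be corrected because it affects a primary safety table with no comparator and the correction costs little.

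**What to change.** - In 8.2, define a laboratory adverse event as a Table 10 grade of at least 1 that is new or worsened from the participant's Day 0 grade.
- Tabulate separately, as shifts or changes from Day 0, the out-of-range Grade 0 values, the ungraded parameters (magnesium, cholesterol) and the ungraded directions (for example high platelets, neutrophils, lymphocytes and Hb), so that none disappears from view.
- Show these by visit, because the unequal number of samples after each dose remains under any counting rule.
- Reconcile the overlapping female Hb limits for grades 1 and 2 in Table 10.
- Reconcile Table 10 with the site-specific grading tables cited in 5.4.2 and Appendix A, or state that they are the same scale.

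The cost is wording in 8.2, a correction within Table 10 and a cross-reference. The Day 0 safety sample is already scheduled, so no new data are needed. The downside is that out-of-range Grade 0 values leave the adverse event table, although they remain listed.
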